### 2.2.1 Intent-to-Treat Effectiveness Population

The Intent-to-treat (ITT) population includes all subjects who were randomized, or FST IV-VI subjects receiving Sculptra Aesthetic re-constituted with 8 mL of SWFI without randomization. All primary and secondary effectiveness variables will be analyzed based on the ITT population.

### 2.2.2 Per-Protocol Effectiveness Population

The Per-Protocol (PP) population includes all ITT subjects who have no protocol deviations considered to have a substantial impact on the primary effectiveness outcome, and will be analyzed according to the randomization scheme. If the PP population contains less than 90% of the subjects in the ITT population, a sensitivity analysis of the primary effectiveness endpoint will be performed based on the PP population.

### 2.2.3 Safety Population

The safety population includes all subjects who were administered the investigational product, and will be analyzed according to as-treated principle. All safety data will be summarized based on the safety population.

## 2.3 Study Subjects

Demographic endpoints and subject characteristics will be summarized using descriptive statistics by treatment group and overall based on the Safety population using the Observed Cases (OC). There are no planned inferential statistical analyses of demographic endpoints or subject characteristics.

### 2.3.1 Subject Disposition

The number of subjects screened will be shown in total and by study center.

The number of subjects in each study population (i.e. ITT, PP, and Safety) will be summarized by study center and in total.

The disposition of subjects will be summarized, including numbers of subjects who were:

- Randomized and unrandomized (i.e. unrandomized FST IV-VI subjects),
- Completed,
- Withdrawn (including primary reason for withdrawal).

 GALDERMA	Title Statistical Analysis Plan 43USSA1705 - New label	Doc id MA-39345
--	--	---------------------------

These numbers will be summarized by study center. The number of subjects expected, completed, missed, and withdrawn will be summarized by scheduled visit.

- Expected all subjects minus withdrawn subjects.
- Completed subjects that showed up at that visit.
- Missed expected subjects minus completed subjects.
- Withdrawn all subjects who have withdrawn up to that visit.

All withdrawn subjects will be listed individually, by subject number, date and reason for withdrawal, and last visit performed.

### 2.3.2 Protocol Deviations

Subjects with any protocol deviations will be summarized overall, by site, and by type.

Depending on the seriousness of the deviation, a subject might be excluded from the PP population, which shall be documented prior to database lock. Reasons for exclusion from the PP population will be summarized.

### 2.3.3 Demographic Characteristics

Age, BMI and baseline [REDACTED] will be summarized as continuous variables. Gender, race, ethnicity, Fitzpatrick skin type, and childbearing potential will be summarized as categorical variables.

### 2.3.4 Medical History, Medications, and Procedures

Prior and concomitant medications will be coded using the World Health Organization Drug Dictionary (WHODD). Medical history, allergen history (food, environmental, and drug), and prior and concomitant procedures/non-pharmacological treatments will be coded according to MedDRA.

Prior medications/procedures are the medications/procedures with stop dates prior to study treatment. Medications/procedures after the study treatment will be considered concomitant.

Subjects reporting medical history, allergen history, cosmetic treatments/procedures, and prior and concomitant procedures/non-pharmacological treatments will be summarized by system organ class (SOC) and Preferred Term (PT).

Subjects reporting prior and concomitant medications will be summarized separately, by WHODD Anatomical Therapeutic Chemical (ATC) Class Level 3 (if Level 3 is not available, the highest class available will be used) and WHODD generic name.

## 2.4 Effectiveness Analysis

### 2.4.1 Datasets Analyzed

All effectiveness variables will be analyzed based on the ITT population. A sensitivity analysis of the primary effectiveness endpoint may be performed based on the PP population. Summary statistics will be computed for each effectiveness endpoint using the Observed Cases (OC) with no imputation for missing data. Inferential statistical analyses will account for missing data as appropriate (SAP Section 2.4.2 below).

	Title Statistical Analysis Plan 43USSA1705 - New label	Doc id MA-39345
--	--	---------------------------

#### 2.4.2 Handling of Missing Data

The number of missing values will be summarized and reported as appropriate.

For ITT analyses of the primary endpoint, missing values will be imputed using the baseline observation carried forward (BOCF) method. The impact of missing data on the primary endpoint will be evaluated by performing a sensitivity analysis based on the observed cases in the ITT population.

All other effectiveness endpoints will be evaluated based on the observed cases in the ITT population.

[REDACTED], if at least 3 of the scale's 5 items are answered, the sum score to be used in the Rausch transformation will be computed as the mean of the completed items times 5.

#### 2.4.3 Primary Effectiveness Analysis

For the 8 mL treatment groups the mean change from baseline in [REDACTED] as assessed by the Blinded Evaluator at Week 48 (denoted as  $\mu$ ) will be evaluated using a one-sided Student's t-test. Thus  $H_0: \mu \geq 0$  will be tested against  $H_1: \mu < 0$  in the right and left side of the face separately. In other words; the null hypothesis of no mean change in [REDACTED] (or possibly a worsening) as compared with baseline will be tested against the alternative hypothesis of an improvement from baseline in [REDACTED]. The test will be performed at the 2.5% significance level. Both right and left sides of the face will need to be statistically significantly less than 0 for the treatment to be judged effective. Results will include one-sided p-values and two-sided 95% confidence intervals for the mean change from baseline for both treatment groups. In order to confirm that there are comparable treatment effects in the two groups, there should be an overlap of the confidence intervals. A figure of these confidence intervals will be given.

As a sensitivity analysis, the above will be repeated using only randomized subjects.

Further, separate summaries and analyses will be created for each skin type and for each site. Consistency across skin types and sites will be explored by using an analysis of variance model. Separate models will be run with effects for 1) treatment, skin type, and treatment by skin type interaction, and 2) treatment, site, and treatment by site interaction.

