4.1 General outline

This is a 48-week, randomized, evaluator-blinded, parallel-group, multi-center, study to evaluate the safety and effectiveness of treatment with Sculptra Aesthetic for correction of NLF contour deficiencies after changes in reconstitution and injection procedures compared to the approved label.

Approximately 64 subjects requiring correction of NLFs will be enrolled and randomized in a 2:1 ratio to treatment with Sculptra Aesthetic reconstituted with 8 mL of SWFI (treatment group) or to Sculptra Aesthetic reconstituted with 5 mL of SWFI (reference group). In addition, eight (8) subjects with FST IV and eight (8) subjects with FST V-VI will be included but not randomized. These subjects will be treated with Sculptra Aesthetic reconstituted with 8 mL of SWFI. When these numbers of FST IV-VI have been treated, any additional FST IV-VI will be randomized in a 2:1 ratio (8 mL:5 mL).

Approximately 60 subjects will be treated with Sculptra Aesthetic reconstituted with 8 mL of SWFI and a reference group of approximately 20 subjects will be treated with Sculptra Aesthetic reconstituted with 5 mL of SWFI as according to the current label.

[REDACTED]

Investigator blinding will be accomplished by using a Treating Investigator to administer the

 GALDERMA	<small>Title</small> 43USSA1705 Sculptra Clinical Study Protocol	<small>Doc id</small> MA-37876
---	--	--

Effective date: 2019-02-21 18:33

treatments and a Blinded Evaluator, to whom randomization and treatment are concealed, to conduct the blinded assessments. In addition, the Blinded Evaluator should not be allowed to retrieve study supplies or be present during the opening of the study supplies or injection procedure. All documents with information regarding study products and randomization assignment should be kept in a separate binder not available to the blinded evaluator. Safety assessments will be performed by non-blinded personnel.

Eligible subjects randomized to receive treatment will be injected by the Treating Investigator at Day 1. The method of injection is at the discretion of the treating Investigator according to Sections 2.2 and 6.6.

Sufficient amount of product should be injected to achieve optimal correction of the NLFs, in the opinion of the Treating Investigator and subject.

Information will be collected about treatment procedure (e.g. injection technique, depth, injection volume, needle sizes, and anesthesia used).

*Effective*

Version: 5.0

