### 1.3 Effectiveness Assessments

For all assessments, baseline will be defined as the observation that is closest to but prior to study treatment on Day 1. Likewise, change from baseline will be calculated as the value at a given time point minus the baseline value.

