## 2 Statistical Methods

### 2.1 General Methods

Any change made to the finalized SAP before database lock will result in a SAP amendment. Otherwise, the change will be documented in the Clinical Study Report (CSR).

Some of the analyses detailed here may be more explicit or in some aspects different from those stated in the protocol. In case of differences, this SAP supersedes the statistical sections in the protocol.

For the study to be deemed successful, the following criteria need to be met:

- The primary effectiveness endpoints (change from baseline in [REDACTED] at Week 48 as assessed by the Blinded Evaluator) should be statistically significantly  $< 0$  on both sides of the face in the treatment group

 GALDERMA	Title Statistical Analysis Plan 43USSA1705 - New label	Doc id MA-39345
--	--	---------------------------

- The confidence intervals around the point estimates of the primary effectiveness endpoints in the treatment group should overlap with those of the reference group
- Acceptable safety profile in the treatment group.

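### The 8 mL versus 5 mL overlap criterion uses unadjusted mean changes although the same-side baseline score is collected; adjusting for it is a modest, nearly free improvement

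*SAP*

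**What the plan says.** SAP 2.1 (General Methods) lists three conditions for success. The first is a significant improvement in the 8 mL arm on both sides of the face. The second is: "The confidence intervals around the point estimates of the primary effectiveness endpoints in the treatment group should overlap with those of the reference group". The third is acceptable safety.

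SAP 2.4.3 gives the method. The 8 mL mean change at Week 48 "will be evaluated using a one-sided Student's t-test", for each side separately, and "The test will be performed at the 2.5% significance level". The output is one-sided p-values and "two-sided 95% confidence intervals for the mean change from baseline for both treatment groups". The between-arm reading then follows: "In order to confirm that there are comparable treatment effects in the two groups, there should be an overlap of the confidence intervals".

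SAP 1.3 defines a baseline for every assessment, and "change from baseline will be calculated as the value at a given time point minus the baseline value". For the overlap criterion, that subtraction is the only use made of the baseline score. The only models with a treatment term are the exploratory analyses of variance in SAP 2.4.3, with skin type or site, and neither contains the baseline score. The randomised-only, observed-case and per-protocol sensitivity analyses (SAP 2.4.3, 2.4.2, 2.2.2) mention no adjustment either. Protocol 10.4 is redacted, but SAP 2.1 says the SAP takes precedence over the protocol's statistical sections where they differ.

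On who is compared, Protocol 4.1 randomises about 64 subjects 2:1 and adds 16 who all receive 8 mL: "In addition, eight (8) subjects with FST IV and eight (8) subjects with FST V-VI will be included but not randomized". SAP 2.2.1 places these 16 in the ITT population.

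**The concern.** The overlap rule is the only readable basis in the plan for saying that the new reconstitution performs like the labelled one. A raw change score implicitly fixes the slope of Week 48 on baseline at 1. If the true slope is lower, subjects with worse folds at baseline improve more whatever the dilution, so a baseline difference between the arms carries over into the observed gap. An 8 mL arm that starts worse looks better than it is, and one that starts better looks worse.

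A baseline difference could arise in two ways: by chance, with only about 20 reference subjects, or through the 16 non-randomised subjects in the 8 mL arm. The randomised-only repeat removes the second source but not the first.

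The direction of the precision effect also matters. Wider intervals overlap more easily, so unexplained baseline variation makes this criterion easier to pass.

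**Working it through.** **Inputs from the documents.** SD of change 1, assumed change -0.74, 15% drop-out (SAP 2.7); about 60 and 20 subjects (Protocol 4.1, SAP 2.7); baseline observation carried forward for the primary ITT analysis (SAP 2.4.2), so all 60 and 20 enter.

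**Assumed, because the documents do not give them.** Correlation rho between baseline and Week 48 of 0.3, 0.5 or 0.7; equal SDs at the two times; normal data.

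**1. The plan's own figures.** One-sample t-test power from the noncentral t, effect 0.74, SD 1, one-sided 2.5%: n = 22 gives 91.1% (n = 21 gives 89.7%) and n = 17 gives 81.7%. Inflation: 22/0.85 = 25.9, so 26; 17/0.85 = 20. All of these agree with SAP 2.7. At n = 60 the same test has 99.99% power, so the 8 mL test against zero needs no covariate.

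**2. What the overlap rule tolerates now.** Half-width = t(0.975, n - 1) x 1/√n: 0.258 (n = 60) and 0.468 (n = 20). With the assumed SD in both arms, the intervals overlap for any observed gap up to 0.258 + 0.468 = 0.726.

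**3. Effect of adjustment on precision.** With equal SDs s, the variance of change is 2s²(1 - rho) = 1, so s = 1/√(2(1 - rho)). The slope of Week 48 on baseline is rho, and the residual SD is s√(1 - rho²) = √((1 + rho)/2). The half-width of the 95% interval for the difference is t x SD x √(1/60 + 1/20), and the root is 0.258. Unadjusted: 1.991 x 1 x 0.258 = 0.51.

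| rho | residual SD | half-width of difference | gap tolerated by overlap |
|---|---|---|---|
| unadjusted | 1 | 0.51 | 0.726 |
| 0.3 | 0.806 | 0.42 | 0.566 |
| 0.5 | 0.866 | 0.45 | 0.608 |
| 0.7 | 0.922 | 0.48 | 0.648 |

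The adjusted half-widths include the small extra term for the observed baseline difference. Part of the fall in the last column comes from pooling the variance across arms: with each arm's own degrees of freedom the adjusted values are 0.586, 0.629 and 0.670. The half-widths for the difference are like for like.

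**4. Effect of a baseline difference.** Shift in the raw gap = (1 - slope) x baseline difference. For 0.5 points: 0.35, 0.25 and 0.15 at rho 0.3, 0.5 and 0.7.

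**5. How often chance produces it.** At rho 0.5, s = 1 and the standard error of the baseline difference is 0.258. A difference of 0.5 or more in one direction has z = 0.5/0.258 = 1.94, probability about 2.6%; 0.25 or more has probability about 17%.

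**6. How often the intervals overlap.** Simulation, one side, 60 and 20 subjects, true gap 0.37 (half the assumed effect):

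| Setting | unadjusted | adjusted |
|---|---|---|
| Balanced, rho 0.3 / 0.5 / 0.7 | about 90% | 82% / 85% / 87% |
| rho 0.5, 8 mL starts 0.5 points worse | about 98% | about 85% |
| rho 0.5, 8 mL starts 0.5 points better | about 64% | about 85% |

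With truly equal arms and balanced baselines, the intervals fail to overlap in just under 1% of trials either way.

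**7. Sensitivity to the assumptions.** If the baseline SD is 1.0, rho is 0.7 and the SD of change is still 1, the Week 48 SD is 1.4 and the slope is 0.7 x 1.4/1.0 = 0.98. The residual SD is then 1.00, with no precision gain and almost no shift. If the baseline SD is 0.7 and rho 0.7, the Week 48 SD is 1.356, the slope is above 1 and the shift changes sign.

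**The case against.** **Criterion 1 already guards the worst case.** A reader might infer that the unadjusted rule could let an ineffective 8 mL preparation be declared comparable, since with balanced baselines the intervals still overlap in nearly half of trials when the true gap is 0.74. The documents do not support that as the headline. With the assumed -0.74 in the reference arm, such a gap means no effect of 8 mL. The first success criterion is a 2.5% test against zero, so with balanced baselines only about 2% of trials pass both criteria on one side, adjusted or not. This objection stands.

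**At a gap of 0.37 the decision changes little.** With balanced baselines at rho 0.5, both criteria are met on one side in about 75% of trials unadjusted and 72% adjusted. This also stands.

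**A material imbalance is not shown to be likely.** Chance gives 0.5 points in one direction only about 2.6% of the time. For the 16 non-randomised subjects to move the mean of 60 by 0.5 points, they would have to start 0.5 x 60/16 = 1.9 points worse on average, and nothing in the documents links skin type to fold depth. The randomised-only repeat removes that source. This stands, although chance imbalance remains in the repeat at about 43 and 21 subjects.

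**The inputs are unseen.** The correlation, the baseline SD, the scale range, most entry criteria and the randomisation section are not readable. The gain is therefore a range that includes almost nothing.

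**Adjustment leaves the larger weakness in place.** Overlap without a margin still tolerates a gap of about 0.61 at rho 0.5, most of the assumed 0.74 effect. This is true and is a separate matter.

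None of this answers the textual point: a success criterion compares two arms on a change score, the baseline is at hand, and no readable analysis uses it as a covariate.

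**Conclusion.** The point holds as a modest weakness in how criterion 2 is estimated. Unadjusted overlap lets any baseline difference feed into the observed gap by (1 - slope) times its size, and may leave the intervals wider than needed. Under SD of change 1, rho 0.3 to 0.7 and equal SDs, adjustment narrows the interval for the difference from 0.51 to 0.42-0.48. It lowers the overlap rate at a true gap of 0.37 from about 90% to 82-87%. Its clearest value is stability: at rho 0.5 a 0.5-point baseline difference moves unadjusted overlap to about 98% or 64%, while the adjusted rate stays near 85%. Such a chance imbalance is uncommon.

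Two stronger readings should be avoided. The documents do not show that the arms will differ materially at baseline, and they do not show that the intervals are too wide; both depend on a slope that is not given, and the gain could be near zero if that slope is close to 1. The one-sample test of 8 mL against zero and its sample size are unaffected.

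**What to change.** In SAP 2.4.3, keep the one-sample t-test for 8 mL. For the comparability criterion and its randomised-only repeat, take the two arm estimates with 95% intervals from an ANCOVA of Week 48 change on treatment and the same side's Blinded Evaluator baseline score. Fit it separately for each side on the same BOCF data set. From the same model, report the 8 mL minus 5 mL difference with its 95% interval. Show the raw means beside the adjusted ones, and point the criterion in SAP 2.1 to the adjusted intervals.

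The cost is a short SAP amendment and one extra model per side, using data already collected. It should be specified in advance: SAP 2.6 notes that the sponsor is not blinded and may analyse data before completion, so a covariate added later could look data-driven.

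The downside is that the overlap criterion becomes slightly harder to meet when the arms truly differ. With equal arms and balanced baselines, the chance of failing it is essentially unchanged. Adjustment does not replace the missing comparability margin, which needs its own decision.

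### The exploratory treatment-by-skin-type interaction in SAP 2.4.3 may be inestimable and is at best very imprecise; rest the skin-type statement on 8 mL estimates and add baseline to both exploratory models (minor)

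*SAP*

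**What the plan says.** SAP 2.4.3 plans separate summaries and analyses for each skin type and each site, and then an exploratory analysis of variance to look at consistency. For skin type: "Separate models will be run with effects for 1) treatment, skin type, and treatment by skin type interaction". A parallel model uses site. Neither list of effects has a baseline term. SAP 1.3 defines the response as the value at the time point minus baseline.

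The darker skin types enter the trial in a particular way. Protocol 4.1: "In addition, eight (8) subjects with FST IV and eight (8) subjects with FST V-VI will be included but not randomized". And: "These subjects will be treated with Sculptra Aesthetic reconstituted with 8 mL of SWFI". FST IV-VI subjects beyond those numbers are randomised 2:1. Protocol 4.1 also gives the planned totals: "Approximately 60 subjects will be treated with Sculptra Aesthetic reconstituted with 8 mL of SWFI and a reference group of approximately 20 subjects". SAP 2.2.1 counts in the ITT population the "FST IV-VI subjects receiving Sculptra Aesthetic re-constituted with 8 mL of SWFI without randomization".

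On how skin type is coded, the visible text offers only SAP 2.3.3: "Gender, race, ethnicity, Fitzpatrick skin type, and childbearing potential will be summarized as categorical variables". Before it turns to the consistency models, SAP 2.4.3 says: "As a sensitivity analysis, the above will be repeated using only randomized subjects".

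**The concern.** A treatment-by-skin-type interaction needs subjects of each skin-type group on both preparations. The skin-type quota can be met in full with nobody of FST IV-VI on 5 mL, because all 16 quota subjects get 8 mL. The Protocol and SAP 1.1.1 set minimum numbers by skin type overall, and no visible text sets one for the 5 mL arm. The model may therefore contain a term that the data cannot estimate, or one that rests on a handful of subjects.

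What is at stake is the statement on whether the result holds across skin types. If the interaction is absent or non-significant because a cell is empty or nearly so, it says little about consistency. Leaving baseline out of a change-score model also gives up precision that the data already collected could supply.

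**Working it through.** **The SAP's own figures first.** SAP 2.7 assumes a change of -0.74, SD 1 and a one-sided 2.5% test. The exact one-sample t-test gives n=22 for 90% power (attained 91.1%) and n=17 for 80% (attained 81.7%). Allowing for 15% drop-out, 22/0.85 = 25.9, so 26, and 17/0.85 = 20. All four SAP numbers reproduce. The SAP states no precision for the interaction.

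**Inputs.** About 64 randomised 2:1, taken as 43 on 8 mL and 21 on 5 mL, plus 16 unrandomised on 8 mL (Protocol 4.1); SD 1 (SAP 2.7). Assumptions: skin type split as I-III versus IV-VI; m additional FST IV-VI subjects on 5 mL, with 2m more on 8 mL; no missing values (SAP 2.4.2 imputes the primary endpoint by BOCF).

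**Cells.** 8 mL IV-VI: 16+2m. 5 mL IV-VI: m. 8 mL I-III: 43-2m. 5 mL I-III: 21-m. These sum to 80, leaving 76 residual degrees of freedom.

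**m=0.** The 5 mL IV-VI cell is empty, the design matrix has rank 3 of 4, and the interaction is not estimable. With three groups (I-III, IV, V-VI), 0 of 2 interaction degrees of freedom are estimable. With six levels, 2 of 5 are, all from within FST I-III (assuming types I, II and III occur in both arms).

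**m of 1 or more.** 95% half-width = t(0.975; 76) × √(sum of 1/cell), with t = 1.992.

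| m | Cells (8 mL IV-VI, 5 mL IV-VI, 8 mL I-III, 5 mL I-III) | Half-width | Power for an interaction of 0.74 (two-sided 5%) |
|---|---|---|---|
| 1 | 18, 1, 41, 20 | 2.12 | 11% |
| 2 | 20, 2, 39, 19 | 1.58 | 15% |
| 4 | 24, 4, 35, 17 | 1.23 | 22% |
| 6 | 28, 6, 31, 15 | 1.09 | 27% |
| 10 (narrowest) | 36, 10, 23, 11 | 1.02 | 30% |

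Using the planned totals of 60 and 20 changes the half-widths by less than 0.02. If 15% of subjects were missing and not imputed, the values at m=1, 2 and 4 would be about 2.30, 1.72 and 1.33. In randomised subjects only (cells 2m, m, 43-2m, 21-m; 60 df) the half-width is 1.82 at m=2 and 1.36 at m=4.

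**Does the 2:1 split matter?** The 5 mL arm alone sets a floor of 1.96 × √(1/m + 1/(21-m)), however the 8 mL arm divides: 2.01 at m=1, 1.46 at m=2, 1.09 at m=4. At m=10 it is 1.96 × √(1/10 + 1/11) = 0.86, still above 0.74.

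**How likely is m=0?** With k additional FST IV-VI subjects under independent 2:1 allocation the chance is (2/3)^k: 20% at k=4 and 9% at k=6. Under blocks of three within FST IV-VI it is 0 for k of 3 or more. The allocation method is blacked out, so both are assumptions.

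**What the 8 mL arm can show at m=0.**
- IV-VI minus I-III (16 versus 43): 1.99 × √(1/16 + 1/43) = 1.99 × 0.293 = 0.58.
- Mean change, IV-VI pooled (n=16): 2.131/√16 = 0.53.
- Mean change, IV or V-VI alone (n=8): 2.365/√8 = 0.84.
- Mean change, I-III (n=43): 2.018/√43 = 0.31.

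**Baseline covariate.** With equal variances at baseline and Week 48 and correlation r, the change score has variance 2(1-r)σ² and the adjusted residual variance is (1-r²)σ², a ratio of (1+r)/2. For assumed r of 0.3 to 0.7 this is 0.65 to 0.85, a reduction of 35% to 15%. Half-widths are multiplied by 0.806 to 0.922: 1.27 to 1.46 at m=2, and 0.99 to 1.13 at m=4.

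**The case against.** A reader might infer that the design rules the interaction out. It does not: additional FST IV-VI subjects are randomised 2:1 and the quotas in SAP 1.1.1 are minima, so there is a route to 5 mL and estimability depends on recruitment. That stands, and every half-width above is conditional on m. Imprecision, however, remains at every m.

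A reader might also infer that the SAP will treat a non-significant interaction as proof of consistency. It says no such thing and attaches no decision rule. The model is called exploratory, and it also contains a skin-type effect, whose 8 mL contrast can be estimated even at m=0. Separate analyses by skin type are already planned, and Fitzpatrick type is tabulated by treatment group, so a sparse cell would be visible. All of this stands and keeps the point minor.

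Nor can one say that the randomised-only sensitivity analysis excludes these models. The sentence in SAP 2.4.3 refers back to what precedes it, and the models come after. But SAP 2.2 ties randomised-only sensitivity analyses to Section 2.4.3 as a whole. The scope is unclear, and applying it here would widen the intervals.

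Skin-type grouping, stratification or an empty-cell rule may be in blacked-out text (Protocol 4.4 and 10.7, part of SAP 2.2), so their absence is not counted as a fault.

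On baseline, an unadjusted analysis of change is legitimate and matches the primary t-tests. The gain rests on a correlation that the documents do not give. Adjustment is an inexpensive improvement, not the repair of an error.

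**Conclusion.** The point holds as a minor one, confined to an exploratory analysis. For FST I-III versus IV-VI the interaction is not estimable at m=0. With SD 1 and a 2:1 split of additional subjects, its 95% half-width runs from 2.12 at m=1 to no less than 1.02. Since that exceeds the whole assumed change of 0.74, even an estimate of exactly zero would leave room for a difference between skin types larger than the expected treatment response. Non-significance therefore could not show consistency. The 8 mL contrast, at about 0.58, is the more informative output and is available whatever m turns out to be.

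Both exploratory models would gain from a baseline covariate by an amount that depends on the assumed correlation; it does not cure an empty or sparse cell. Nothing here touches the primary t-tests, the sample size or the success criteria in SAP 2.1.

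**What to change.** In SAP 2.4.3:

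- **(a)** Base the skin-type statement on the 8 mL mean changes with 95% confidence intervals for FST I-III, IV and V-VI, and for IV-VI pooled, together with the 8 mL difference IV-VI minus I-III and its interval.
- **(b)** Report the treatment-by-skin-type interaction for I-III versus IV-VI only if FST IV-VI subjects are present on 5 mL, as an estimate with 95% interval and the four cell counts. Otherwise state that it is not estimable. State that non-significance is not read as consistency. Keep IV and V-VI separate in the descriptive results so that pooling does not hide a difference between them.
- **(c)** Add the Blinded Evaluator's same-side baseline score as a covariate in both the skin-type and the site model, and show the unadjusted result alongside, because the non-randomised subjects may differ at baseline.

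It would also help to say whether the randomised-only sensitivity analysis extends to these models.

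The cost is a few sentences in a SAP amendment, for which SAP 2.1 provides before database lock. No new subjects, visits or data are needed: the baseline score is already collected, and analyses by skin type are already planned.
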